#### E. SUMMARY OF ANALYSES

**Table 1** contains the list of analytic datasets that are needed to isolate the effect of particular study design choices, explained below. The risk window is constant and set at days 1-28 following incident study drug dispensing for all analyses.

- 1. Assess use of a pre-exposure vs. post-exposure comparison window to demonstrate the impact and trade-offs of using an unexposed referent window compared to a later post-exposure reference window. The timing of the windows is always relative to the day of the incident study exposure (i.e., Day 0).
- Assess the impact of a 183-day outcome washout that seeks to preserve statistical power, compared to 400-day outcome washout that improves ability to detect truly incident outcomes. Outcome incidence is always assessed relative to the date of the outcome event.
- 3. Assess the incidence definition of the health outcome at either the 4th vs. 5th level of the MLCCS tree to improve that ability to detect only incident outcomes.
- 4. Assess the additional value of surveillance for outcomes that are primarily occurring in ambulatory encounter settings. Inclusion of such outcomes may allow for capture of conditions that will later become more serious and require hospitalization but may also add alerts that are not serious enough to warrant further consideration.

- 6 -

Analytic	Study Exposure	Comparison	Outcome	Tree	Outcome Encounter Settin
Dataset ID		Window	Incidence	Level	
1	1 (levetiracetam)	[-56,-29]	183	4	IP, ED
2	1 (levetiracetam)	[-28,-1]	183	4	IP, ED
3	1 (levetiracetam)	[36,63]	183	4	IP, ED
4	1 (levetiracetam)	[-56,-29]	400	4	IP, ED
5	1 (levetiracetam)	[-28,-1]	400	4	IP, ED
6	1 (levetiracetam)	[36,63]	400	4	IP, ED
7	1 (levetiracetam)	[-56,-29]	183	5	IP, ED
8	1 (levetiracetam)	[-28,-1]	183	5	IP, ED
9	1 (levetiracetam)	[36,63]	183	5	IP,ED
10	1 (levetiracetam)	[-56,-29]	400	5	IP,ED
11	1 (levetiracetam)	[-28,-1]	400	5	IP,ED
12	1 (levetiracetam)	[36,63]	400	5	IP,ED
13	1 (levetiracetam)	[-56,-29]	400	4	IP, ED, AV
14	1 (levetiracetam)	[-28,-1]	400	4	IP, ED, AV
15	1 (levetiracetam)	[36,63]	400	4	IP, ED, AV
16	2 (lamotrigine)	[-56,-29]	183	4	IP, ED
17	2 (lamotrigine)	[-28,-1]	183	4	IP, ED
18	2 (lamotrigine)	[36,63]	183	4	IP, ED
19	2 (lamotrigine)	[-56,-29]	400	4	IP, ED
20	2 (lamotrigine)	[-28,-1]	400	4	IP, ED
21	2 (lamotrigine)	[36,63]	400	4	IP, ED
22	2 (lamotrigine)	[-56,-29]	183	5	IP, ED
23	2 (lamotrigine)	[-28,-1]	183	5	IP, ED
24	2 (lamotrigine)	[36,63]	183	5	IP,ED
25	2 (lamotrigine)	[-56,-29]	400	5	IP,ED
26	2 (lamotrigine)	[-28,-1]	400	5	IP,ED
27	2 (lamotrigine)	[36,63]	400	5	IP,ED
28	2 (lamotrigine)	[-56,-29]	400	4	IP, ED, AV
29	2 (lamotrigine)	[-28,-1]	400	4	IP, ED, AV
30	2 (lamotrigine)	[36,63]	400	4	IP, ED, AV
31	3 (calibration)	[-56,-29]	183	4	IP, ED
32	3 (calibration)	[-28,-1]	183	4	IP, ED
33	3 (calibration)	[36,63]	183	4	IP, ED
34	3 (calibration)	[-56,-29]	400	4	IP, ED
35	3 (calibration)	[-28,-1]	400	4	IP, ED
36	3 (calibration)	[36,63]	400	4	IP, ED
37	3 (calibration)	[-56,-29]	183	5	IP, ED
38	3 (calibration)	[-28,-1]	183	5	IP, ED
39	3 (calibration)	[36,63]	183	5	IP, ED
40	3 (calibration)	[-56,-29]	400	5	IP, ED
40	3 (calibration)	[-28,-1]	400	5	IP, ED
41 42	3 (calibration)	[36,63]	400	5	IP, ED
42	3 (calibration)	[-56,-29]	400	4	IP, ED, AV
43	3 (calibration)	[-28,-1]	400	4	IP, ED, AV
44	3 (calibration)	[36,63]	400	4	IP, ED, AV

#### Table 1. Full List of Analytic Datasets for Two Study Exposures and One Calibration Exposure

Notes: IP = Inpatient Setting; ED = Emergency Department Setting; AV = Ambulatory Care Setting. Risk Window is set to Days 1-28 for all analytic datasets.

An example analytic dataset is shown with simulated data in **Table 2**. The Analytic Dataset ID is directly mapped to the list above. The original diagnosis captures the incident ICD-9-CM or ICD-10-CM code captured prior to mapping and the leaf level node represents the mapped value. The time of the outcome is relative to the incident study drug exposure that is always indexed as Day 0. The number of counts is the number of times this particular code was observed with this particular relative timing in the study.

Table 2. Sample Analytic Bataset with Simulated Bata						
Analytic	Original	Original	Leaf Level	Leaf Level	Relative Time	Counts
Dataset ID	Diagnosis	Diagnosis Type	Node	Node Type	of Outcome	
1	250	9	250	9	-15	3

#### Table 2. Sample Analytic Dataset with Simulated Data

#### F. STATISTICAL METHODS

Most analytic datasets created will be analyzed with two versions of TreeScan, Information Component Temporal Pattern Discovery, and Sequence Symmetry Analysis. Sequence Symmetry Analysis is not intended to be used with a post-exposure comparison window and these scenarios will not include this analytic technique.

#### 1. TreeScan:

We will use both the conditional and unconditional Bernoulli tree-based scan statistic that detects elevated frequencies of outcomes in pre-specified time periods. We do not plan on testing the tree-temporal scan statistic although the data collected could be repurposed in a separate project. TreeScan™ (www.treescan.org) is a data mining method that scans electronic health data that are organized into clinically relevant groupings of medical product exposures or health outcomes. With respect to the self-controlled risk interval design, TreeScan has been evaluated in simulation environments. as well as empirical environments. For a pre-defined exposure, it adjusts for the multiple testing inherent in evaluating thousands of potential adverse events to assist with prioritization of alerts or statistically significant findings for further investigation.

Two versions of the Bernoulli test statistic are planned for this evaluation, and both rely on the computation of the log likelihood ratio for each outcome node *LLR(G)*. The test statistic *T* is the maximum log likelihood ratio across all observed nodes. For hypothesis testing using *T*, the p-value is derived non-parametrically using Monte Carlo simulation. Under the null hypothesis, there is no association between the study exposure and any outcomes. If the null hypothesis is true, each event within a node is expected to occur in relationship to the length of the risk and comparison windows. The conditional version of the test statistic adjusts this probability by accounting for the overall pattern of outcomes in both windows (see equations below). In both versions, when performing Monte Carlo simulations, all nodes must contain the same total number of outcomes per node as observed in the original data. They are assigned to occur across the observation window per the null hypothesis to derive the test statistic used to generate an alert (i.e., a statistically significant departure from the null hypothesis).

- 8 -

Equation 1a (Unconditional): LLR = 
$$\ln\left(\frac{\left(\frac{c_G}{c_G + n_G}\right)^{c_G} \left(\frac{n_G}{c_G + n_G}\right)^{n_G}}{(p)^{c_G}(1-p)^{n_G}}\right) I\left(\frac{c_G}{c_G + n_G} > p\right)$$

$$Equation \ 1b \ (Conditional): LLR = \ln\left(\frac{\left(\frac{C_G}{C_G + n_G}\right)^{c_G} \left(\frac{n_G}{C_G + n_G}\right)^{n_G}}{\left(\frac{C}{C + N}\right)^{c_G} \left(\frac{N}{C + N}\right)^{n_G}}\right) I\left(\frac{c_G}{c_G + n_G} > \frac{C}{C + N}\right)$$

Equation 2:  $T = {}^{\max}_{G} LLR(G)$ 

Where: T = Bernoulli tree scan statistic

- G = node of interest
- $c_{\mathsf{G}}$  = number of outcomes in the risk window for a given node  $\mathsf{G}$
- $n_{G}$  = number of outcomes in the comparison window for a given node G
- p = ratio of the risk window length to the entire observation window length
- C = total number of outcomes in the risk window across ALL nodes
- N = total number of outcomes in the comparison window across ALL nodes

*I()* is the indication function, which is 1 when there are more outcomes in the risk window than would be expected by chance. It is included to ensure that we are looking for an excess risk of the having the adverse event rather than a protective decreased risk.

We will use an alerting threshold of p=0.01. In other words, we will evaluate nodes with log-likelihood ratios that fall into the top 1% of the maximal log-likelihood ratios observed using Monte Carlo. These nodes represent the most extreme departures from the null hypothesis.

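### Equation 1b omits the outside-node factors of the conditional log likelihood ratio, so if it is computed as printed, broad nodes are scored too low by about their own share of all events

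*Protocol*

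**What the plan says.** Protocol section III.F.1 plans an unconditional and a conditional Bernoulli statistic and states that "both rely on the computation of the log likelihood ratio for each outcome node". The test statistic T (Equation 2) "is the maximum log likelihood ratio across all observed nodes".

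- Equation 1a (unconditional) compares the node's observed split with a fixed p, defined as "p = ratio of the risk window length to the entire observation window length".
- Equation 1b (conditional) is Equation 1a with p replaced by C/(C+N) and 1−p by N/(C+N). The text explains the change thus: "The conditional version of the test statistic adjusts this probability by accounting for the overall pattern of outcomes in both windows".
- The totals are defined as "C = total number of outcomes in the risk window across ALL nodes" and "N = total number of outcomes in the comparison window across ALL nodes".

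In Equation 1b, numerator and denominator carry only the exponents c_G and n_G. No factor has the exponents C−c_G and N−n_G. Nothing else in the protocol supplies such a factor or says that C/(C+N) is to be treated as a known constant. (A capital C_G appears in the Equation 1b numerator in the text read from the PDF. It may be a reading artefact, and nothing here rests on it.)

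**The concern.** In Equation 1a, p is fixed by the window lengths. Events outside the node then have the same likelihood under both hypotheses and cancel, so an inside-only formula is correct.

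In Equation 1b the reference proportion is estimated from all events, including those of node G. If G has an excess, it pulls C/(C+N) up. Under the alternative the rest of the tree then has its own, lower fitted proportion, (C−c_G)/(C+N−c_G−n_G), and its likelihood no longer cancels. An inside-only formula is therefore not the log likelihood ratio that the text says it is.

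The omission grows with the size of the node, and T is a maximum over nodes ranging from single codes to whole body systems. At stake are the ranking and detection of broad nodes in one of the two TreeScan versions, in a study whose purpose is to compare methods on alerts and power.

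**Working it through.** **Inputs.** The risk window is 28 days ("The risk window is constant and set at days 1-28 following incident study drug dispensing for all analyses") and every comparison window in Table 1 is 28 days, so p = 28/56 = 0.5. The alert threshold is 0.01, for excess risk only. The top tree level has 18 body systems (section III.C), an average share of 1/18 = 5.6%. The protocol gives no event totals, node shares or power, so there is no planned figure to reproduce; those inputs are assumed and varied below.

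**1. The full ratio.** Write m = c_G+n_G, M = C+N, f = m/M, p0 = C/M. Under the null all events share p0. Under the alternative the node has c_G/m and the rest has (C−c_G)/(M−m). Then

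full LLR = (Equation 1b) + (C−c_G)·ln{[(C−c_G)/(M−m)]/p0} + (N−n_G)·ln{[(N−n_G)/(M−m)]/(1−p0)}.

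**2. Size of the missing part.** Let d = c_G − m·p0. To second order:

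- inside part (Equation 1b) ≈ d²/[2m·p0(1−p0)]
- outside part ≈ d²/[2(M−m)·p0(1−p0)], because the rest of the tree deviates by −d
- sum = inside × [1 + m/(M−m)] = inside/(1−f)

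Hence printed/full ≈ 1−f.

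**3. Numerical check, 20,000 background events split evenly between the windows.**

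- Node with 20% of background, rate ratio (RR) 1.17: c_G = 2,000×1.17 = 2,340, n_G = 2,000, C = 10,340, N = 10,000, f = 4,340/20,340 = 0.213. Printed 8.25, full 10.49, ratio 0.786 (1−f = 0.787).
- Node with 30% of background, RR 1.15: c_G = 3,450, n_G = 3,000, C = 10,450, N = 10,000, f = 6,450/20,450 = 0.315. Printed 7.37, full 10.76, ratio 0.685 (1−f = 0.685).

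With M = 10,000 and RR 1.5:

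| f | printed | full | shortfall |
|---|---|---|---|
| 1% | 1.97 | 1.99 | 1.0% |
| 5% | 9.09 | 9.57 | 5.0% |
| 10% | 16.34 | 18.14 | 9.9% |
| 20% | 25.86 | 32.27 | 19.8% |
| 30% | 29.77 | 42.40 | 29.8% |

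**4. Does Monte Carlo calibration offset it?** Simulation on assumed 18-system trees, with node totals and C held fixed in the null replicates. The protocol states the first condition ("all nodes must contain the same total number of outcomes per node as observed in the original data"); the second is assumed. The 1% critical value of T hardly changes between printed and full: 8.86 vs 8.87 and 8.78 vs 8.80 (M = 10,000), 7.72 vs 7.75 (M = 2,000). Small nodes drive it, so the shortfall at a broad node is not recovered.

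**5. Power at an elevated body-system node, printed → full.** Effects were set near the limit of detection: RR 1.22 to 1.58 for M = 10,000, 1.57 to 2.93 for M = 2,000, and 1.155 to 1.28 for 20,000 background events.

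| Share (approx.) | M = 2,000 | M = 10,000 | 20,000 background |
|---|---|---|---|
| 5% | 78.1 → 80.9% | 74.7 → 78.3% | 32 → 35% |
| 10% | 74.6 → 80.4% | 65.9 → 73.6% | 33 → 41% |
| 20% | 65.7 → 80.3% | 59.0 → 78.0% | 36 → 56% |
| 30% | 61.0 → 85.3% | 45.9 → 76.6% | 39 → 73% |

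The tabulated losses are about 3 to 4, 6 to 8, 15 to 20 and 24 to 34 points. Further runs, not tabulated, put the upper ends at about 5, 9 and 23 points for shares of 5%, 10% and 20%.

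**6. Comparison with the unconditional statistic.** In the two cases of step 3, Equation 1a gives 13.33 and 15.71. The part of the gap between unconditional and printed conditional that is due to the missing factors is (10.49−8.25)/(13.33−8.25) = 44% and (10.76−7.37)/(15.71−7.37) = 41%.

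**The case against.** The case on the other side has five parts.

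- **Conditioning itself costs sensitivity.** A reader might infer that conditional TreeScan would look less sensitive than unconditional TreeScan, or than Information Component Temporal Pattern Discovery (ICTPD), because of the formula. The documents do not support that. Step 6 shows that more than half of the gap to the unconditional version remains with the full ratio. With 20,000 background events, a 30% share, RR 1.155 and a critical value of 8.6, power is 95% unconditional, 74% full conditional and 41% as printed. ICTPD uses an external, node-specific reference and has no explicit multiplicity control, so it differs for unrelated reasons. This part stands.
- **The loss is confined to a band of effects.** With 20,000 background events and RR 1.25, printed vs full power is about 95 to 97% vs 99% at a 20% share and 99% vs 100% at 30%. The protocol fixes no effect sizes for its simulation. This stands.
- **Large shares are assumed.** An average body system holds 5.6%, where the loss is a few points. The simulation inserts risk into selected outcomes rather than a whole body system, and at narrow nodes the difference is negligible. This stands.
- **The software may not use the printed formula.** The analysis is to be run in TreeScan, and the protocol does not show what that program computes. This stands: the harm is conditional.
- **Validity is not affected.** A reader might infer invalid p-values or false alerts. The p-value ranks the same statistic in observed and simulated data, so the 1% level holds.

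None of this restores the missing factors. Equation 1b defines a planned analysis and is not the quantity the text names.

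**Conclusion.** The point holds in a limited form. Equation 1b, as printed, is not the conditional log likelihood ratio, and it understates that ratio by about the node's share of all events. This follows from algebra and needs no assumption about the data.

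The consequence does rest on assumptions: that the formula is computed literally, that null replicates hold C fixed, and the tree shapes, event totals and effects used above. Under these, the power loss at a broad node is about 3 to 5 points at a 5% share, 6 to 9 at 10% and 15 to 23 at 20%, and more beyond. It is negligible for nodes holding about 1% or less and for strong effects. Type I error is unaffected. If the software already uses the full ratio, the error is confined to the protocol's formula. This is a minor correction, worth making because the protocol is meant to define and compare methods.

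**What to change.** In Equation 1b:

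- multiply the numerator by [(C−c_G)/(C+N−c_G−n_G)]^(C−c_G) × [(N−n_G)/(C+N−c_G−n_G)]^(N−n_G);
- make the denominator [C/(C+N)]^C × [N/(C+N)]^N;
- keep the indicator as it is.

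Define C and N so that each event is counted once, for example as totals over the leaves. The nodes are nested and section III.C says that some branches have fewer levels, so a literal sum over every node would weight events unequally.

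State that the conditional analysis is run with this statistic, after checking what the software computes. The cost is one corrected equation and that check. The Monte Carlo procedure and the 1% threshold stay as they are. The part of the sensitivity difference from the unconditional version that comes from conditioning will remain, and the report should say so.

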#### 2. Information Component Temporal Pattern Discovery:

Information Component Temporal Pattern Discovery (ICTPD) is another longitudinal signal detection method that can be applied to self-controlled designs. ICTPD uses a shrinkage estimator to reduce the number of false positives due to random variability (and then indirectly the multiple comparisons) or due to very low expected values for rare adverse events or exposures. It does not explicitly control for multiplicity. The information component with shrinkage  $IC_{\Delta}$  can be calculated as shown below. The more general formula allows for accounting of censoring between the risk window and control window, but this study will require overall enrollment in both. There is a closed form solution for the credibility interval of the  $IC_{\Delta}$ .

$$IC_{\Delta} = \log_2 \left( \frac{y_1 + \frac{1}{2}}{y_0 \left( \frac{E_1}{E_0} \right) + \frac{1}{2}} \right)$$

Where:  $y_1$  = number of outcomes in the risk window among study exposure of interest

 $y_0$  = number of outcomes in the comparison window among study exposure of interest

 $E_1$  = number of outcomes in the risk window among the external calibration exposure of interest

 $E_{0}$  = number of outcomes in the comparison window among the external calibration exposure of interest  $% \left( {{E_{0}}} \right) = {E_{0}} \right)$ 

ICTPD makes use of an external calibration mechanism to control for global patterns of healthcare utilization that may account for systematic differences between pre- and post- exposure windows. It has a similar intention to the conditional Bernoulli version of the tree scan statistic described above but is implemented differently. The conditional Bernoulli version of the tree-based scan statistic utilizes the pattern of outcome occurrence in the entire MLCCS tree to control for global patterns of healthcare. The ICTPD uses an external exposure group – specifically, all exposures using all dispensing or prescription

records – and then performs the adjustment in a node-specific fashion. Using node-specific notation similar to the equations above, the  $IC_{\Delta}$  can be re-written below:

$$IC_{\Delta} = \log_2\left(\frac{c_G + \frac{1}{2}}{n_G\left(\frac{C_G}{N_G}\right) + \frac{1}{2}}\right)$$

where: G = node of interest

 $c_{\rm G}$  = number of cases in the risk window for a given node G among the study exposure of interest

 $n_{G}$  = number of cases in the comparison window for a given node G among the study exposure of interest

 $C_{G}$  = total number of cases in the risk window for a given node G among the calibration exposure population

 $N_G$  = total number of cases in the comparison window for a given node G among the calibration exposure population

In our study, access to all dispensing records (i.e., a "general" population) is not feasible so we will randomly select 100 NDC and HCPCS codes and combine their data to create our "calibration exposure."

The traditional alerting threshold for the ICTPD method uses a 2-sided 95% credible interval, denoted  $IC_{\Delta 025}$ . An alert occurs only when this value is positive, implying that an alert is only raised for an unusual elevation in the frequency of observed outcomes in the risk window. The indication function in the test statistic for TreeScan performs the same function. For this analysis, we will observe the number of alerts when  $IC_{\Delta 025} > 0$  and when  $IC_{\Delta 01} > 0$ .

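### ICTPD's node-level calibration ratio is left unstabilised: it fails at zero counts and can raise alerts without any excess where calibration outcomes are few

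*Protocol*

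**What the plan says.** Protocol section III.F.2 presents the information component as a shrinkage estimator. Its aim is to limit false positives from chance, "ICTPD uses a shrinkage estimator to reduce the number of false positives due to random variability", and also those "due to very low expected values for rare adverse events or exposures". The node-level formula is IC = log2[(c_G + 1/2) / (n_G·C_G/N_G + 1/2)]. Here c_G and n_G are the study drug's risk- and comparison-window counts, and C_G and N_G are the same counts in the calibration exposure. N_G is defined as the "total number of cases in the comparison window for a given node G among the calibration exposure" population.

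The section describes the method's usual calibration group as all exposures on record, and says that it "and then performs the adjustment in a node-specific fashion". Because that group is not available, "we will randomly select 100 NDC and HCPCS codes and combine their data". The formula is otherwise unchanged. An alert is a positive lower bound, counted at 2.5% and again at 1%. The interval is cited as having a closed form but is not printed. No rule is given for zero calibration counts, no minimum count, and no expected size of the calibration exposure.

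Section III.G records total alert load for the empirical assessment. Section III.F.3 sets the SSA cut-off at the larger of the TreeScan and ICTPD alert counts.

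**The concern.** The 1/2 stabilises c_G and the whole expected count, but not the ratio inside it. With calibration drawn from every dispensing, a node's ratio would be nearly free of random error. With 100 codes, cut by tree level, washout, care setting and 28-day window (Table 1), some nodes may hold few calibration outcomes. The error of C_G/N_G then passes undamped into the expected count, and an interval that treats the expected count as known ignores it.

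At stake is the fairness of the comparison. Conditional TreeScan adjusts with whole-tree totals and is not exposed to this noise. Alerts caused by the calibration sample would be counted against ICTPD, and could lengthen the SSA list in the pre-exposure scenarios where SSA is run.

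**Working it through.** The protocol states no ICTPD error rate or calibration count, so there is no figure to reproduce.

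**Inputs.** The formula and thresholds are from III.F.2. All windows in Table 1 are 28 days, so the null ratio is taken as 1. Assumed: Poisson counts; m study events and M calibration events per window (ranges shown); and the interval Gamma(c_G + 1/2, rate E + 1/2) with E = n_G·C_G/N_G treated as fixed.

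**1. Zero cells.** With Poisson mean M, P(N_G = 0) = e^(−M): 37%, 14% and 5% at M = 1, 2, 3. P(C_G = 0 and N_G ≥ 1) = e^(−M)(1 − e^(−M)): 23%, 12% and 5%. In the first case IC has no value. In the second E = 0.

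**2. Single nodes.**
- C_G = 0, c_G = 4, n_G = 20: IC = log2(4.5/0.5) = 3.17; lower bounds +1.43 (2.5%) and +1.06 (1%). It alerts at both thresholds although events fell five-fold.
- C_G = 0, c_G = n_G = 3: lower bounds +0.76 and +0.31, an alert with no excess. With c_G = n_G = 1 or 2 there is no alert, so the 1/2 gives some protection.
- C_G/N_G = 1/3, c_G = n_G = 10: E = 3.33; bounds +0.42 and +0.21, an alert. With 5/10, E = 5 and the 2.5% bound is −0.10, no alert.

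**3. Why relative size matters.** The log of C_G/N_G has standard error of about √(1/M + 1/M). At M = 5 this is √0.4 = 0.63; at M = 200 it is √0.01 = 0.10. The study drug's own log ratio at m = 20 has √0.1 = 0.32. The calibration error dominates in the first case and is minor in the second.

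**4. Null alert rates.** 300,000 simulated nodes per setting, true ratio 1, 2.5% bound, undefined nodes counted as no alert:

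| Calibration events per window | m = 5 | m = 20 | m = 100 |
|---|---|---|---|
| ratio known exactly | 8.5% | 8.2% | 8.3% |
| 50 | 8.7% | 11.2% | 20.5% |
| 20 | 9.7% | 15.1% | 28.0% |
| 10 | 11.1% | 19.8% | 33.5% |
| 5 | 14.2% | 25.7% | 37.9% |

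Only the rise above the first row is due to calibration. The baseline exceeds 2.5% mainly because n_G is itself random but treated as known. At the 1% bound and m = 20, the rate is 5.1% with an exact ratio and 15.7% at M = 10, so the stricter threshold does not cure it. At m = 20, the share of alerts with c_G ≤ n_G is 29% at M = 5, 18% at M = 10 and about 1% at M = 50.

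**5. Where the effect disappears.** With M = 10m the rates are 3.3% against 3.1% (m = 1), 8.7% against 8.4% (m = 5), 9.0% against 8.2% (m = 20) and 9.2% against 8.2% (m = 100). With one study event per window the rate stays at 3 to 4% for M from 1 to 200.

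**The case against.** The strongest reply is that the harm depends on counts the protocol does not give. A reader might infer that ICTPD's alert load as a whole reflects calibration noise. The documents do not support that: 100 pooled codes may yield many more outcomes per node than one study drug, and step 5 shows almost no inflation then. The largest figures, 26% and 38%, need 4 to 20 times fewer calibration than study events in a node. This stands, and it limits the point to nodes where calibration counts are not well above study counts.

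The gamma interval is assumed because the protocol only cites its own. This also stands: the alert rates are illustrative. The undefined ratio at N_G = 0 and the collapse at C_G = 0 follow from the printed formula alone.

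A zero-cell convention could sit in an analysis plan not at hand, and undefined nodes do not add alerts. That answers N_G = 0 in part. It does not answer C_G = 0 or small counts, where the printed rule returns a misleading value.

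Finally, III.G intends each method to be used broadly as in practice, and the 100-code compromise is disclosed. That is a reason to keep the printed version in the report, not to omit a check on it.

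**Conclusion.** The point holds in a limited form. As printed, the calibration ratio is not stabilised by the 1/2, has no value at N_G = 0, and at C_G = 0 can signal an excess where events fell. Under the assumed interval and a true ratio of 1, null alerts at 20 study events per window rise from about 8% to 11%, 20% and 26% at 50, 10 and 5 calibration events per window. The rise is larger in bigger study nodes and near nil once calibration counts are about ten times study counts. How many nodes are affected, and so how far the total alert load and the SSA cut-off move, cannot be determined from the protocol. Section III.F.2 should be amended before the methods are compared, because the formula gives wrong answers in cases that the change of calibration group makes possible.

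**What to change.** In III.F.2:

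1. Compute IC025 and IC01 with the calibration ratio's uncertainty carried through, for example by drawing the ratio as Gamma(C_G + 1/2) / Gamma(N_G + 1/2). This also defines the zero cells. Report it beside the printed version, so that ICTPD as used in practice is still evaluated.
2. Report C_G and N_G for every alerting node, and give the ICTPD alert load with and without nodes below a calibration count fixed in advance.
3. State which ICTPD count (2.5% or 1%, printed or modified) enters the SSA cut-off in III.F.3.

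In simulation with a true ratio of 1, 5 to 200 calibration events and 1 to 100 study events per window, change 1 kept null alerts at about 3 to 8%.

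Two simpler repairs are not enough. Adding 1/2 to C_G and N_G without carrying the uncertainty leaves 17.8% null alerts at 10 study and 5 calibration events, against 8.4% with an exact ratio. Shrinking toward the whole-tree ratio with weight 10 leaves about 21% at 100 study events and 5 to 20 calibration events. It is also worse than the raw ratio where a node's background differs from the tree's: with a true node ratio of 1.5, a tree ratio of 1, 20 study events and 5 calibration events, about 35% against 27%. It would also blur the node-specific adjustment that sets ICTPD apart from conditional TreeScan.

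The cost is protocol wording and a few lines of code, with no new data. Power falls in nodes with few calibration events: for a three-fold effect at 20 study events, about 63% against 94% at 10 calibration events and 97% against 99% at 50. The higher figures belong to the printed rule with its inflated null alert rate, so the comparison is not like for like.

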Only incident exposures of interest will be ascertained, and incidence will be defined as the first oral drug dispensing in 183 days. Patients will be required to be free of any form of the exposure of interest (e.g., intravenous, oral). Exposures of interest will be identified by National Drug Codes (NDCs) and Healthcare Common Procedure Coding System (HCPCS) codes listed in a separate code list document.

Enrollment is required to assess exposure incidence. Enrollment gaps of 45 days or less will be bridged, i.e., treated as continuously enrolled time.

[figure not shown]
Figure 1 is a visual guide to the various parameters that govern how the study cohort is created.

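### The ICTPD calibration ratio is a raw node-level fraction from 100 sampled codes that the shrinkage does not protect: zero counts break the statistic, and sampling error raises alert rates by an amount that cannot be fixed

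*Protocol*

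**What the plan says.** All references are to Protocol section III. Under F.2 (Information Component Temporal Pattern Discovery), the node statistic is log2 of (c_G + 1/2) over (n_G × C_G/N_G + 1/2). Here c_G and n_G are the study drug's risk-window and comparison-window counts, and C_G and N_G are the matching calibration counts. N_G is a plain count: "total number of cases in the comparison window for a given node G among the calibration exposure population".

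The calibration group is described as "specifically, all exposures using all dispensing or prescription" records, and the method "performs the adjustment in a node-specific fashion". Because full access is not feasible, the protocol substitutes a sample: "we will randomly select 100 NDC and HCPCS codes and combine their data to create our" calibration exposure. The stated safeguard is that "ICTPD uses a shrinkage estimator to reduce the number of false positives due to random variability" and very low expected values.

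Alerts are counted when the lower 2.5% limit, and separately the lower 1% limit, of the credible interval exceeds zero. The interval is said to have a closed form and is given by reference only. Section F.3 lets the larger of the TreeScan and ICTPD alert counts set how many SSA outcomes are examined. Section G makes total alert load a recorded result.

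**The concern.** With all dispensing records, C_G/N_G is close to a known constant in most nodes. With 100 pooled codes spread over the nodes of a tree covering thousands of outcomes, it is an estimate and can be a poor one in thin nodes. The formula treats it as a plain number. The shrinkage meant to guard against very low expected values is added after the ratio has been applied, so a thin calibration node can itself create a very low expected value.

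At stake is the comparison of methods. If ICTPD's alert load depends partly on how many events the calibration sample supplies, that part of the contrast with TreeScan reflects the sample and not the method. In the pre-exposure scenarios an inflated ICTPD count can also lengthen the SSA list.

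**Working it through.** **Inputs.** The formula, calibration source and two thresholds come from F.2. The risk window is 28 days, and each comparison window in Table 1 is also 28 days, so the null ratio is 1 when there is no utilisation trend.

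**Assumptions.** (i) The interval is the Gamma posterior implied by the two 1/2 terms: shape c_G + 1/2, rate E + 1/2, with E = n_G × C_G/N_G held fixed. A node alerts when the lower quantile exceeds 1. (ii) Null counts are Poisson: c_G and n_G with mean m, C_G and N_G with mean k × m. The protocol does not give k, so a range is shown.

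**Step 1. The plan's own levels (0.025 and 0.01).** With E known exactly, the null alert rate is 2.2%/0.8% at E=20, 2.3%/0.9% at E=100 and 2.5%/1.0% at E=1000. The thresholds behave as labelled only when the whole expected count is exact.

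**Step 2. Zero cells.** The first two bullets follow from the printed formula alone.
- N_G=0: C_G/N_G has no value, so the statistic is undefined.
- C_G=0, N_G>0: E=0 for any n_G. With c_G=3 and n_G=50 the statistic is log2(3.5/0.5) = 2.81. With a ratio of 1 it would be log2(3.5/50.5) = −3.85.
- Under assumption (i), the limits for c_G=3 and E=0 are the Gamma quantiles at shape 3.5 divided by 0.5, which are 1.69 and 1.24. Both exceed 1, so both thresholds alert. For c_G=1 or 2 neither does.
- Frequency, with an expected calibration count of a per window: P(N_G=0) = e^(−a), which is 37%, 14%, 5% and 0.7% at a = 1, 2, 3 and 5. P(C_G=0, N_G>0) = e^(−a)(1 − e^(−a)), which is 23%, 12%, 5% and 0.7%.

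**Step 3. Null alert rate per node, all four counts random** (200,000 simulated nodes per setting; IC025/IC01):

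| k (calibration ÷ study count) | m = 50 | m = 100 |
|---|---|---|
| ratio known exactly | 8.2%/5.0% | 8.3%/5.0% |
| 20 | 8.6%/5.4% | 8.8%/5.5% |
| 10 | 9.0%/5.8% | 9.1%/5.8% |
| 2 | 12.3%/8.6% | 12.5%/8.6% |
| 1 | 15.6%/11.5% | 15.8%/11.7% |
| 0.5 | 20.2%/16.1% | 20.4%/16.3% |
| 0.2 | 27.9%/24.2% | 28.1%/24.5% |

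**Step 4. Large-count check.** The interval allows for variance m in c_G − E, whereas the actual variance is about m(2 + 2/k). The rate is therefore about 1 − Φ(z/√(2 + 2/k)).
- Ratio known: 1.96/√2 = 1.386, giving 8.3%; 2.326/√2 = 1.645, giving 5.0%.
- k=1: 1.96/2 = 0.98, giving 16.4%; 2.326/2 = 1.163, giving 12.2%.

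Both agree with the table.

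**Step 5. Splitting the causes (m=100).** With n_G random and the ratio exact, the rate is 8.3%/5.0%. With only the ratio random and n_G replaced by its mean, it is 2.7%/1.2% at k=20, 7.5%/4.5% at k=2, 11.9%/8.1% at k=1 and 26.8%/23.1% at k=0.2. The fixed-n_G assumption is the larger source at high k. Calibration error is the larger at k of about 1 or below.

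**The case against.** The strongest counter-argument is that most of the baseline excess, from 2.5% to about 8%, comes from treating n_G as fixed. That is part of the method under evaluation and has nothing to do with the 100 codes. This stands.

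A reader might infer that ICTPD alert load would mostly reflect calibration noise. The documents do not support that. One hundred codes are not one hundred events, pooled user and event numbers are not stated, and calibration counts 10 to 20 times the study counts would add only about one point.

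The interval appears only by citation. If it carries the error in all counts, Step 3 falls away, while the undefined cell at N_G=0 and the zero expected count at C_G=0 remain. Zero-count handling might also sit in an analysis plan that is not shown. Even so, the protocol itself fixes the formula, the calibration source and the thresholds.

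The thresholds are credible limits, the protocol admits that ICTPD has no explicit multiplicity control, and it claims no false-alert rate. It would be wrong to say that a stated error rate is breached.

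A reader might also infer that sampling by code lets continuing users of the same ingredient count as new starters. The protocol does not say how incidence applies to the calibration codes, and for exposures of interest it states "Patients will be required to be free of any form of the exposure of interest". That reading is not established.

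The SSA effect is limited. ICTPD matters there only when its count exceeds TreeScan's, only as a list length, and not with post-exposure windows.

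**Conclusion.** The point holds in a limited form. The formula fails in sparse calibration nodes: it is undefined at N_G=0, and at C_G=0 with N_G>0 it ignores the study drug's comparison count. Under the assumed Gamma interval, every such C_G=0 node with at least 3 risk-window cases alerts at both thresholds.

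Under that interval and Poisson counts, the null alert rate per node is about 8%/5% even with a perfect ratio. It is about 12–16%/9–12% when calibration counts are one to two times the study counts, about 20%/16% at half and 28%/24% at one fifth. Where this study falls in the range cannot be settled from the protocol. Differences between drugs within the 100 codes would add variance that is not modelled here.

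This is worth amending because alert load is a recorded result and can set the SSA cut-off. It does not undermine a methods evaluation that is expressly not a safety assessment.

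**What to change.** 1. Compute the ratio as (C_G + 1/2)/(N_G + 1/2). When C_G or N_G is below a floor set in advance, use the parent node's ratio or flag the node as not evaluable for ICTPD. Half-counts alone remove the undefined cells but not the excess alerts, since they hardly change the ratio's sampling error at moderate counts.
2. Next to the native IC025 and IC01 alerts, report alerts from an interval that carries all four counts: log[(c+1/2)(N+1/2)/((n+1/2)(C+1/2))] with variance 1/(c+1/2) + 1/(n+1/2) + 1/(C+1/2) + 1/(N+1/2). Under the null at a study mean of 20 and k of 1 to 10, it alerts at 2.2–2.4% and 0.8–0.9%. At a mean of 100 it alerts at about 2.4–2.5% and 0.9–1.0%.
3. Report calibration counts per node, so that readers can see where the ratio is thin.

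**Cost.** Protocol wording and a short formula change, using counts already planned for collection. The half-counts and fallback are a small departure from the published formula. The four-count interval is conservative in sparse nodes: at a study mean of 5 its IC025 rate is 0.7–1.6% for k from 0.5 to 10. It also loses detection there. With a risk ratio of 3, a mean of 5 comparison events and tenfold calibration counts, detection at IC025 falls from about 80% to 49%. It should therefore supplement the native alert and not replace it.

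Redrawing the calibration sample by ingredient in proportion to users is not proposed. It would need user counts across all products, and the protocol says access to all dispensing records is not feasible.
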